Significance: There is an acute and immediate need for the development of safe, effective, and non-habit forming pharmacological treatments for chronic pain disorders. Very large numbers of OEF/OIF Veterans report chronic pain symptoms (as many as 50% or higher). Current medications such as opiates that are frequently used to treat chronic pain symptoms have side effect risks such as respiratory depression, addiction, sedation, and potentially lethal interactions with other drugs. The proposed projects could lead to new therapeutic avenues that are safe, non-habit-forming, and effective. Neurosteroids demonstrate pronounced analgesic actions, and preclinical and clinical data suggest that these molecules hold promise for chronic pain disorders. New agents for the treatment of chronic pain could markedly improve long-term outcome and quality of life in OEF/OIF Veterans.

Relevance to Veteran Health: There is currently a paucity of safe and effective agents for the treatment of chronic low back pain, a disorder that impacts large numbers of OEF/OIF Veterans and is frequently accompanied by PTSD and other comorbid symptoms. Pregnenolone may represent an effective, safe, well-tolerated, immediately accessible, and inexpensive treatment for these symptom domains, potentially leading to improved functional outcome and quality of life in OEF/OIF Veterans with chronic pain disorders.

RESEARCH DESIGN AND METHODS

The proposed randomized controlled trial (RCT) will investigate adjunctive pregnenolone as a potential analgesic in OEF/OIF Veterans with chronic low back pain. This will be a 4-week, randomized, double-blind placebo-controlled pilot study preceded by a one-week placebo lead-in period (all participants). Proposed sample size estimates are 45 patients per group (it is estimated that up to 120 Veterans will be randomized in order to obtain the sample size of 45 participants per group).

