Experimental Design: The proposed design is a randomized, double-blind, two-arm trial of pregnenolone and placebo to determine the possible analgesic effects in OEF/OIF Veterans with chronic low back pain. The total study duration is 8 weeks (6 study visits followed by two-follow up phone calls). All patients will monitor pain symptoms for one week with pain diaries, followed by a 1-week placebo-only lead-in period, 90 subjects will be randomly assigned to one of two groups. Of these subjects, 45 subjects will receive pregnenolone, and 45 subjects will receive placebo for 4 weeks (in addition to the taper period of 5 days). Patient interview assessments and laboratory studies will be performed at each interview time point. Pregnenolone, allopregnanolone and other neurosteroid metabolites will be determined by gas chromatography / mass spectrometry (GC/MS), proceeded by high performance liquid chromatography (HPLC). Those subjects randomized to pregnenolone will receive this neurosteroid on the following schedule:

- Pain symptom monitoring with pain diaries for 1 week, then
- Placebo lead-in phase 0 mg in two doses (0 mg, PO, BID) for 1 week, then
- Pregnenolone 100 mg in divided doses (50 mg, PO, BID) for 1 week, then
- Pregnenolone 300 mg in divided doses (150 mg, PO, BID) for 1 week, then
- Pregnenolone 500 mg in divided doses (250 mg, PO, BID) for 2 weeks.

Dosing: Pregnenolone fixed escalating up to 500mg/day will consist of the following schedule:

Visit 1 (week 0, screening visit) and pain symptom assessment

Visit 2 (week 1) placebo lead-in (all participants)

Visit 3 (week 2, baseline visit): 50mg PO, BID x 1 week,

Visit 4 (week 3): 150mg PO, BID x 1 week,

Visit 5 (week 4): 250mg PO, BID for two weeks.

Visit 6 (week 6): No medication will be dispensed; study medication will be tapered by 100mg per day and then discontinued. The FDA has reviewed this protocol and issued an Investigational New Drug number (IND #114,799) for this randomized controlled trial utilizing the pregnenolone doses above for low back pain, and has provided a formal permission to proceed letter for this study. In addition, [name] (the PI's primary mentor on this VA funded Career Development Award) currently holds FDA IND numbers for the use of pregnenolone for treatment of schizophrenia (IND #71,768), PTSD (IND #73,099) and TBI (IND #78,270).

Methodology for Neurosteroid Identification and Quantification:

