Any incident regarding theft/loss of data, authorized access of sensitive data or storage devices or non-compliance with security controls will be addressed according to VA policy (VHA Handbook 1200.05, 10j; 1058.01 11.a; 6500, Appendix D and 6500.2) and will be reported to Durham VAMC PO and ISO immediately using the following: [contact].

Study members who are initially part of the study team, but leave the study team for whatever reason will no longer have access to participant study data.

DATA ANALYSIS AND STATISTICAL CONSIDERATIONS

Statistical Methods

Analysis of treatment effects will use the mixed-models approach to repeated-measures analysis of variance (SAS Institute, Cary, NC) with baseline and endpoint scores as dependent variables, time as a within-subject repeated measure, and treatment group (pregnenolone or placebo) as a between-subjects fixed factor. The primary analyses for this will be based on an intention-to-treat principle that will include in the analyses all randomized subjects. The primary efficacy outcome variable is the weekly mean of the average pain scores (0 – 10 numeric rating pain score recorded daily from patient) after study drug initiation. These are obtained over time, and thus we will use mixed effects models with random intercepts to account for subject effects and the correlation among repeated measurements within a subject. Models will be developed which include as independent variables the treatment group and the baseline pain score. Thus, the effect of the intervention will be assessed by examining the significance of the slope β_1 coefficient for intervention in the following model:

$$P_{it} = \beta_0 + b_{0i} + \beta_1 Int + \beta_2 BaseP + \beta_3 t + e_{it}$$

where P_{it} is the mean weekly pain score for the i^{th} individual at time point t , β 's denote fixed effects, b_{0i} is the random intercept for the i^{th} individual, and e 's are random errors. Patients who are withdrawn from the study because of side effects will only be included in outcome assessments in which they participated. The mixed effects models can handle incomplete panels of information. All tested hypotheses will be considered statistically significant if the 2 sided p value is ≥ 0.05 unless otherwise specified.

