Secondary analyses will include the following assessments. Assessment of changes in mood, anxiety, sleep, working memory, executive function, and pain interference (BDI, DTS, Tower of London, Digit Sequencing Task, BPI interference, PGI, AIS) will be analyzed via a repeated measures analysis similar to analyses for primary outcome assessments. Categorical analyses of patient response (30% improvement, 50% improvement) will be evaluated via a comparison of proportions using Fisher's exact test. Time to event analyses will also be performed, to examine the time to 30% and time to 50% reduction in 24 hour average pain score, using daily pain score data. These analyses will be performed by calculating Kaplan-Meier survival curves. Changes in physical function, mental health, cognitive symptoms and back pain-related disability will be assessed using ANCOVA models. Safety will be assessed by comparing the incidence of major and minor side effects (defined in human subjects section below) in the study drug vs. placebo groups, using Fisher's exact tests. Path analysis will be used to perform a preliminary assessment of whether any pain reduction effect is independent of possible effects of study drug on anxiety and mood.

Missing data: The mixed models used to evaluate the continuous response variables are able to handle moderate amounts of missing data provided they are missing at random. We will examine the missing at random

assumption by assessing differences between dropouts and completers on baseline as well as response variables up to point of premature withdrawal. If the missing at random assumption does not appear to be tenable, we will report the mixed models results but spend additional effort characterizing treatment effect at time of premature withdrawal.

[figure not shown]
Power Analysis and Sample Size Determination:

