The effect of pregnenolone on low back pain will be evaluated using several statistical methods. This clinical trial design will compare two randomly assigned groups (pregnenolone or placebo) with respect to self-reported lower back pain measured on a 0-10 pain scale. Inclusion criteria for the study require that all participants report pain severity of at least 4/10. Given the low back pain often presents as long periods of low-level intensity pain punctuated by periods of acute exacerbation, it is quite likely that the mean pain level for selected participants will substantially exceed 4/10. Thus for power calculations, we assume a baseline mean pain level of six for each group. We also assume a standard deviation of 1.0 since we have little information to support any specific value in this population.

For the purpose of power calculations we assume that the mean pain levels of the two independent groups will be compared using a Two-Sample T-Test, Null Hypothesis: $\text{Mean1}=\text{Mean2}$. Alternative Hypothesis: $\text{Mean1}<>\text{Mean2}$. The standard deviations were assumed to be unknown and equal.

Assuming specified numbers of participants in each group (N) the mean differences detectable for at least 80% power and $\alpha=0.05$ are shown in the following table and figure.

N1	Mean1	Mean2
4	6.0	3.6
5	6.0	3.8
6	6.0	4.0
6	6.0	4.2
8	6.0	4.4
10	6.0	4.6
12	6.0	4.8
17	6.0	5.0
26	6.0	5.2
45	6.0	5.4
100	6.0	5.6

Group sample sizes of 45 achieve at least 80% power to detect a difference of 0.6 between the null hypothesis that both group means are 6.0 and the alternative hypothesis that the mean of group 2 is 5.4 with estimated group standard deviations of 1.0 and 1.0 and with a significance level (alpha) of 0.05000 using a two-sided two-sample t-test. Using this experimental group size should yield sufficient power to detect clinical meaningful effects.

Data Collection: Data pertaining to psychiatric rating and other assessment scales will be collected on hard copy and data pertaining to laboratory values will be collected in manners used for the VA Mid-Atlantic MIRECC Registry. A study number identifying clinical and biological data will be the only number to appear on data and documents used for evaluation or statistical analysis. This data will be kept in locked file cabinets accessible only to qualified personnel.

REFERENCES

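### The opening sentence of Statistical Methods makes baseline an outcome, against the primary-outcome sentence and printed equation, where it is only a covariate

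*Combined protocol and SAP*

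**What the plan says.** All of the primary analysis text is in one paragraph, under Data Analysis and Statistical Considerations, Statistical Methods.

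- The opening sentence, on analysis of treatment effects in general, calls for a repeated-measures mixed model "with baseline and endpoint scores as dependent variables, time as a within-subject repeated measure".
- The primary variable is then the weekly mean of the "numeric rating pain score recorded daily from patient) after study drug initiation".
- On covariates: "Models will be developed which include as independent variables the treatment group and the baseline pain score". The printed equation has treatment (Int), BaseP and time t on the right-hand side, plus a random intercept. It has no treatment-by-time term.
- On the test: "the effect of the intervention will be assessed by examining the significance of the slope" coefficient β1 in that equation.

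The next paragraph says that mood, trauma symptoms, sleep, cognition and pain interference "will be analyzed via a repeated measures analysis similar to analyses for primary outcome assessments".

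The baseline time point is labelled differently in different places. Dosing has "Visit 3 (week 2, baseline visit): 50mg PO, BID x 1 week". Study Timeline item 5 attaches baseline to Visit 1, in a sentence about laboratory tests. The Table 1 header appears to put it at Visit 2, though that may be an artefact of how the table was read. Study Timeline item 4 starts the diary at Visit 1 and the single-blind placebo lead-in at Visit 2.

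**The concern.** Baseline cannot be both a response in the model and the covariate BaseP without changing what β1 means. A pre-randomization row carries no treatment effect. If it is stacked with the post-drug rows and a single main effect is fitted, that effect is averaged over weeks in which treatment could act and a week in which it could not. The reported difference and its confidence interval would then describe a diluted quantity, and a reader would have no sign of it.

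Two further gaps make the wording matter. First, the placebo lead-in capsules are handed out at Visit 2, as study medication in a single-blind phase. A programmer could therefore take study drug initiation to mean Visit 2 and count the lead-in week as an outcome row. Second, the limit to scores after study drug initiation is written only for the pain score. Most of the repeated-measures secondary scales are collected at all six visits (Study Timeline item 10), and the only sentence that names their dependent rows is the opening one.

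**Working it through.** **Inputs.** From Power Analysis and Sample Size Determination: 45 per arm, SD 1.0, difference 0.6, two-sided 0.05. From Experimental Design: four weeks of randomized treatment. The documents give no within-subject correlation, so I assume equal correlation r between weeks of 0.3, 0.5, 0.7 or 0.8. I also assume complete data and, at first, a constant effect over the four weeks.

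**The plan's own figure.** "Group sample sizes of 45 achieve at least 80% power to detect a difference of 0.6". The noncentrality is 0.6/√(2/45) = 2.85 on 88 degrees of freedom, which gives power 0.804. With 44 per arm it is 0.795. So 45 reproduces. It rests on a two-sample t-test and does not depend on the conflict examined here.

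**Algebra.** With complete, balanced data, β1 in the random-intercept model is the coefficient from regressing each subject's mean outcome on Int and BaseP. If baseline is also an outcome row, the subject mean is

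(BaseP + k × post-drug mean)/(k+1).

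The BaseP part is fitted exactly by the BaseP covariate and adds nothing to the treatment coefficient. Hence β1 = k/(k+1) × the covariate-adjusted post-drug effect:

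- k = 4: 4/5 × 0.60 = 0.48
- k = 1: 1/2 × 0.60 = 0.30

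The residuals of the subject means shrink by the same factor, so the t statistic is unchanged unless the random-intercept variance is estimated at zero.

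**Simulation** (1,500 trials per cell, random-intercept REML with linear time; entries at r = 0.3 / 0.5 / 0.7 / 0.8):

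| Outcome rows, BaseP in model | Mean β1 | 95% CI contains 0.6 (%) | Power |
|---|---|---|---|
| Four post-drug weeks (printed equation) | 0.60 / 0.61 / 0.60 / 0.60 | 97 / 96 / 95 / 95 | 0.995 or more (noncentral t) |
| Baseline + four weeks | 0.48 / 0.49 / 0.48 / 0.48 | 80 / 81 / 74 / 65 | same as row above to three decimals |
| Baseline + one endpoint | 0.30 / 0.30 / 0.30 / 0.30 | 24 / 15 / 4 / 1 | 0.75 / 0.87 / 0.97 / 0.996 |

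The comparator for the last row is final-week ANCOVA, with power 0.84 / 0.90 / 0.98 / 0.997. The loss is 9 points at r = 0.3 and small elsewhere. It arises because the random-intercept variance is estimated at zero in every two-row trial.

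**Lead-in week as an outcome row.** With BaseP from the diary-only week, the average over five rows is (0 + 4 × 0.60)/5 = 0.48. In simulation (3,000 trials each, same assumptions) the interval contained 0.6 in 75 to 85% of trials, with power 0.97 to above 0.99. If the lead-in week also supplied BaseP, β1 was again 0.48, with coverage 67 to 79%.

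**Dropout.** Research Design and Methods says "it is estimated that up to 120 Veterans will be randomized in order to obtain the sample size of 45 participants per group", which implies 30/120 = 25%. Assume 60 per arm and dropout completely at random, spread evenly over the four weeks. The printed equation stays at 0.59 to 0.61. Baseline plus four weeks falls to 0.45 to 0.46. Baseline plus one endpoint falls to 45/(60+45) × 0.6 = 0.26.

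**Which week is BaseP.** The diary starts at Visit 1, so Visit 1 itself cannot supply a weekly diary mean. Two candidates remain: the diary-only week (Visits 1 to 2) and the lead-in week (Visits 2 to 3). Both precede randomization.

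**The case against.** The strongest reply is that the specific text governs the general. The opening sentence is about treatment effects at large. The lines after it name the primary variable, restrict it to scores after study drug initiation, list the covariates, print the equation and identify the tested coefficient. On that reading no baseline row enters the primary model, β1 recovers 0.60, and one stray clause does no harm.

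Most of this stands. A reader might infer from the opening sentence that nothing in the plan keeps baseline out of the outcome. That is not so, because the primary-outcome sentence does. A reader might also infer that planned power is lost. A main-effect test on baseline and endpoint rows without BaseP would have power of only 0.42 / 0.37 / 0.33 / 0.32, but no section specifies that model: β1 is tested in an equation that contains BaseP. A treatment-by-time test on the same two rows recovers 0.60, though the plan names no such term.

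The reply does not remove the clause, tie study drug initiation to the first randomized dose, or settle the rows for the secondary analyses. It also does not name the BaseP week, although either candidate is valid.

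**Conclusion.** The plan contradicts itself on the role of baseline in its primary analysis rule, and the opening sentence is the part that is wrong. The printed model on the four post-drug weeks is sound. The consequence of following the opening sentence with BaseP and β1 retained is a diluted estimate: 0.48 in place of 0.60 with four weeks, 0.30 with one endpoint, and 0.48 if the lead-in week is counted. The test changes little. The k/(k+1) factor is exact for complete data and does not depend on the correlation. The coverage and power figures rest on the assumed correlations and a constant effect.

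The printed model should not be taken as at least as powerful as every alternative. That holds under a constant effect, but the dose escalates over the first weeks. If the effect were proportional to dose (assumed 0.12, 0.36, 0.60, 0.60), β1 would average 1.68/4 = 0.42. Power would be 0.89 / 0.90 / 0.96 / 0.99, against 0.84 / 0.90 / 0.98 / 0.997 for final-week ANCOVA. Nor do the documents show that the analysis will be run wrongly. This is a wording error worth correcting because it leaves open a choice between analyses that report different effects from the same data.

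**What to change.** 1. In Statistical Methods, delete the clause that makes baseline and endpoint scores the dependent variables.
2. State that P_it consists of the four weekly means after the first randomized dose (Visit 3 onward), and that baseline enters only as BaseP.
3. Name the pre-randomization diary week that supplies BaseP, and reconcile the baseline labels in Dosing, Table 1 and Study Timeline item 5.
4. For the repeated-measures secondary analyses, use the same form, with the pre-randomization score as a covariate. If baseline is kept as an outcome row, test the treatment-by-time contrast and not the main effect.

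The cost is wording only. The printed equation, the β1 test and the sample size of 45 per arm stay as they are, and no new data are needed. Either choice of BaseP week is valid, because both weeks precede randomization.

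### The significance rule is inverted: as written, a two-sided p value of 0.05 or larger counts as significant

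*Combined protocol and SAP*

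**What the plan says.** Under Data Analysis and Statistical Considerations, the Statistical Methods section sets one rule for the whole trial: "All tested hypotheses will be considered statistically significant if the 2 sided p value is ≥ 0.05 unless otherwise specified". The same paragraph judges the primary effect by the significance of the intervention coefficient (beta 1) in the mixed model for weekly mean pain, so the rule decides the primary claim.

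The secondary and safety analyses that follow (repeated-measures models, ANCOVA, and Fisher's exact tests for responders and side effects) carry no threshold of their own. The rule allows for exceptions, but the plan states none.

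The section Power Analysis and Sample Size Determination works to the usual convention. It says "Group sample sizes of 45 achieve at least 80% power to detect a difference of 0.6", "and with a significance level (alpha) of 0.05000 using a two-sided two-sample t-test".

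**The concern.** In a test at the 5% level, a two-sided p value of 0.05 or more means that the null hypothesis is not rejected. The sentence gives the label of significance to exactly those results and withholds it from results below 0.05. The power section's alpha of 0.05 requires the opposite, so the two sections cannot both be followed.

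At stake is the pre-specified criterion for the primary efficacy claim and for each secondary and safety hypothesis that is tested. Against the conventional rule, every label of significant or non-significant would be swapped.

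**Working it through.** **Inputs, all from the combined protocol and SAP**

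- Decision rule as written: significant if two-sided p ≥ 0.05 (Statistical Methods).
- Alpha 0.05, two-sided two-sample t-test (Power Analysis and Sample Size Determination).
- 45 per group, means 6.0 and 5.4, so a difference of 0.6 (same section). The 1:1 allocation is confirmed under Experimental Design.
- SD 1.0 in each group, which the plan describes as an assumption: "We also assume a standard deviation of 1.0 since we have little information to support any specific value in this population".
- Variances: "The standard deviations were assumed to be unknown and equal", so the t distribution applies.

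**Step 1. Reproduce the plan's own figure under the conventional rule (reject when p < 0.05)**

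- Degrees of freedom = 2n − 2 = 2 × 45 − 2 = 88.
- Noncentrality = difference / (SD × √(2/n)) = 0.6 / (1.0 × √(2/45)) = 0.6 / 0.2108 = 2.846.
- Two-sided 5% critical value of t with 88 degrees of freedom = 1.987.
- Power = P(|T| > 1.987), where T is noncentral t with these values, = 0.8037, or 80.4%.

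This agrees with the stated figure of at least 80%, and 45 is the smallest group size that reaches 80%. The same formula returns the tabulated N in all 11 rows of the plan's table. A one-sided test would give 88.1% at n = 45, so the calculation is two-sided, as the plan says. The sample size was therefore built on rejection at small p values.

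**Step 2. Apply the rule as written (declare significance when p ≥ 0.05)**

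- No true effect: the p value is uniform on 0 to 1, so P(p ≥ 0.05) = 1 − 0.05 = 0.95.
- True difference of 0.6: P(p ≥ 0.05) = 1 − 0.8037 = 0.1963.

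**Step 3. Compare the two rules**

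| Truth | Declared significant, p < 0.05 | Declared significant, p ≥ 0.05 (as written) |
|---|---|---|
| No effect | 5.0% | 95.0% |
| Difference 0.6, SD 1.0, 45 per group | 80.4% | 19.6% |

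**Step 4. Sensitivity to the SD**

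The second row depends on an SD for which the plan claims little support. With 45 per group and a difference of 0.6:

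| Assumed SD | p < 0.05 | p ≥ 0.05 (as written) |
|---|---|---|
| 1.0 | 80.4% | 19.6% |
| 1.5 | 46.7% | 53.3% |
| 2.0 | 29.1% | 70.9% |
| 2.5 | 20.3% | 79.7% |

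The SDs above 1.0 are illustrative and do not come from the plan. The 95% in the first row of step 3 does not depend on the SD.

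**The case against.** The best reply is that this is a reversed sign and not an intended rule. The power section states the null, the two-sided alternative and the significance level, and its whole table follows from p < 0.05, so the plan itself shows what was meant. No competent analyst would act on the sentence, and harm arises only if someone does. On intent this is right. It does not settle the matter: the power section is written for sample-size purposes and for the pain comparison alone, while the faulty sentence is the only one that covers all hypotheses. A reader should not have to infer the success criterion from a power calculation.

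Four narrower points have some force.

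- **The error is probabilistic.** The literal rule goes wrong in 95% of trials with no effect and in 80.4% of trials at the planned effect, not in all of them.
- **It reaches tested hypotheses only.** The time-to-event analysis is described as survival curves with no named test, and the path analysis as preliminary with no named test.
- **The 80.4% and 19.6% are illustrative.** They belong to a t-test with SD 1.0. The primary analysis is a baseline-adjusted repeated-measures mixed model whose power the plan does not give.
- **The text was read from a PDF by a program.** The same sign is rendered sensibly elsewhere, for example in the pain-score entry criterion, so nothing suggests a misreading. The source PDF should still be checked.

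**Conclusion.** The concern holds. The only p-value threshold in the plan is inverted and contradicts the plan's own alpha. Followed literally, it gives a 95% false-positive rate instead of 5%. At the planned alternative it would give a 19.6% chance of declaring a real effect instead of 80.4%.

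The first figure needs only a valid p value. The second rests on the power section's inputs (two-sample t-test, difference 0.6, SD 1.0, 45 per group). The conclusion assumes that the sign in the source PDF is as shown here. It must be corrected because it governs the primary claim, even though the intended direction is plain.

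**What to change.** Check the sign in the source PDF. Then change ≥ 0.05 to < 0.05 in the last sentence of the model paragraph under Statistical Methods, keeping its scope over all tested hypotheses and its allowance for stated exceptions. A sign of ≤ 0.05 would also be consistent with the stated alpha; choose one and use it throughout.

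The cost is one character in a document amendment. The corrected rule restores a 5.0% type I error and, on the plan's inputs, 80.4% power, so the target of 45 per group stands. The model, data collection and trial conduct are unaffected.

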- The first secondary outcome measure will be the Brief Pain Inventory (BPI) (Severity and Interference scores). The BPI is a self-reported scale that measures the severity of pain and the interference of pain on function. The scores range from 0 (no pain) to 10 (pain as severe as you can imagine). There are 4 questions assessing worst pain, least pain, average pain in the past 24 hours, and the pain right now (As described above average pain scores will be used in the primary outcome measure). The Interference scores range from 0 (does not interfere) to 10 (completely interferes). There are 7 questions assessing the interference of pain in the past 24 hours for general activity, mood, walking ability, normal work, relations with other people, sleep, and enjoyment of life. Questions from the BPI will be asked at each patient visit.
 - The Tower of London is a clinician administered subtest from the BAC-A which measures executive functioning.
 - Digit Sequencing Task is a clinician administered subtest from the BAC-A which measures working memory.
 - The Davidson Trauma scale is a self-report questionnaire that measures trauma symptoms.

Routine laboratory assessments will be completed at each visit (CBC, Chem 7, GI panel) and will require the patient to donate approximately 10ml of blood. Additional blood samples will be collected for serum analysis during all study visits. Serum samples will be frozen in a -80 degree freezer. Upon completion of the study, samples will be thawed and analyzed using Gas Chromatography/Mass Spectrometry. Patients will receive an ECG at Visit 1 and the final study visit. Vital signs will be assessed and recorded at each study visit.

Additional assessment measure descriptions are listed below.

Study Timeline:

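### About 13 secondary efficacy comparisons are each called significant at an unadjusted two-sided 0.05; separately, BPI Severity, a declared secondary, has no named analysis

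*Combined protocol and SAP*

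**What the plan says.** Under Data Analysis and Statistical Considerations, Statistical Methods, the decision rule reads: "All tested hypotheses will be considered statistically significant" if the "2 sided p value is ≥ 0.05 unless otherwise specified". Nothing else in the supplied text specifies otherwise for the clinical secondaries. There is no adjustment, no testing order, no dependence on the primary result and no exploratory label.

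The secondary outcomes appear in two places.

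- **Secondary Outcome Measures:** "The first secondary outcome measure will be the Brief Pain Inventory (BPI) (Severity and Interference scores"), followed by Tower of London, Digit Sequencing Task and the Davidson Trauma Scale (DTS). That is four instruments and five scores.
- **Statistical Methods, secondary analyses:** seven outcomes are named for one method: "BDI, DTS, Tower of London, Digit Sequencing Task, BPI interference, PGI, AIS) will be analyzed via a repeated measures analysis". The paragraph adds 30% and 50% responder rates by Fisher's exact test, Kaplan-Meier curves for time to 30% and 50% pain reduction, and ANCOVA on four domains (physical function, mental health, cognition and back-related disability). No instruments are named for those domains.

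**The concern.** The plan uses a single word, significant, for every test. Under that rule, one small p value among many secondaries carries the same label as the primary result, whatever the primary shows. The background sections hope for benefit in pain, PTSD and TBI symptoms, while the sample size is justified for pain alone. A lone result on mood, sleep or cognition could therefore be reported as a significant finding when it is a chance one.

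The second problem is which outcomes make up the secondary set. BPI Severity belongs to the outcome named first among the secondaries but is missing from the analysis list. BDI, PGI, AIS, the responder rates and the ANCOVA domains are analysed but are not in the declared list. No multiplicity procedure can be applied until the set is fixed.

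**Working it through.** **1. The plan's own figure.** Power Analysis and Sample Size Determination gives: "Group sample sizes of 45 achieve at least 80% power to detect a difference of 0.6". Its inputs are an SD of 1.0 and two-sided alpha 0.05. By the normal approximation, n per arm = 2 × (1.960 + 0.842)² × 1.0² / 0.6² = 43.6, so 44. The two-sample t-test gives 44.6, so 45, with power 80.4% at 45. The figure reproduces. It covers one test; the plan gives no error rate for the secondaries.

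**2. Reading the rule.** Taken literally, "2 sided p value is ≥ 0.05 unless otherwise specified" is reversed. The power section works "with a significance level (alpha) of 0.05000 using a two-sided two-sample t-test", so the intended threshold is taken to be two-sided 0.05. Each test then has a 5% chance of a false result in either direction and 2.5% in the drug's favour.

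**3. Counting tests.** Seven repeated-measures outcomes + two responder rates + four ANCOVA domains = 13. The two time-to-event analyses would make 15, but only Kaplan-Meier curves are specified and no between-group test is named, so 13 is the safer count.

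**4. Independent tests.**
- Either direction: 1 − 0.95^13 = 1 − 0.513 = 0.487.
- Benefit only: 1 − 0.975^13 = 1 − 0.720 = 0.280.

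**5. Correlated tests.** The documents give no correlations, so a common value ρ is assumed. With c = 1.96, k tests and a shared normal factor x:
- Either direction: 1 − ∫ φ(x) [Φ((c − √ρ x)/√(1−ρ)) − Φ((−c − √ρ x)/√(1−ρ))]^k dx.
- Benefit only: 1 − ∫ φ(x) [Φ((c − √ρ x)/√(1−ρ))]^k dx.

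The table gives the chance of at least one nominally significant result when there is no effect on any outcome.

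| Tests | Direction | ρ = 0 | 0.3 | 0.5 | 0.7 |
|---|---|---|---|---|---|
| 7 (repeated measures only) | either | 30% | 27% | 23% | 18% |
| 7 | benefit | 16% | 14% | 11% | 9% |
| **13** | **either** | **49%** | **42%** | **33%** | **24%** |
| **13** | **benefit** | **28%** | **21%** | **17%** | **12%** |
| 15 (if time-to-event is tested) | either | 54% | 46% | 36% | 26% |
| 15 | benefit | 32% | 23% | 18% | 13% |

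**6. Why these are upper figures for a given count.** The 50% responders are a subset of the 30% responders. The ANCOVA cognition domain may repeat the two cognitive subtests already counted. Fisher's exact test with 45 per arm has an actual two-sided size of about 2.6% to 3.0% for response rates of 20% to 50%, not 5%. The count itself could rise if an ANCOVA domain were tested on more than one score, which the plan leaves open.

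**7. Comparing the lists.**

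| Outcome | Declared secondary | Named analysis |
|---|---|---|
| BPI Severity | yes | none |
| BPI Interference, Tower of London, Digit Sequencing, DTS | yes | repeated measures |
| BDI, PGI, AIS | no | repeated measures |
| 30% and 50% response | no | Fisher's exact test |
| Four ANCOVA domains | no | ANCOVA, instruments not named |

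**The case against.** The best defence is that this is a self-described pilot with one primary variable, and nowhere does the plan say that a secondary p value can support a claim if the primary fails. Unadjusted secondary tests are ordinary in such a trial if they are labelled exploratory. It is true that the primary's alpha is not touched and that the plan is silent on what a secondary result would support. But the plan does attach the term significant to every test. It also marks other work as exploratory (pharmacogenetics) or preliminary (the path analysis) without doing so here. If the secondaries are exploratory, the plan has to say so.

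Four stronger readings are tempting, and the documents do not support them.

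- **A null drug has a one-in-three to one-in-two chance of a significant benefit.** The rule is two-sided, so those are roughly the either-direction rates. One in three for benefit would need about 16 independent tests and one in two about 28; at most about 15 comparisons are listed.
- **The mismatch between the lists inflates the error rate.** It does not. The number of unadjusted tests does; the mismatch is a separate defect.
- **The added outcomes were not prespecified.** BDI, AIS and PGI are scheduled in Table 1 and in the Study Timeline, and are named with a method in the secondary analyses. They are only absent from the declared secondary list.
- **The leading secondary has no planned test.** BPI Interference is tested; only Severity is left out. Nor does the primary stand in for Severity: the primary is a bedtime diary score averaged over the week, whereas BPI Severity comes from four pain questions asked at visits.

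**Conclusion.** The concern holds as two separate points.

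First, with 13 secondary efficacy comparisons each judged at two-sided 0.05 and no true effect, the chance of at least one false benefit is 12% to 28%. That is about 5 to 11 times the 2.5% that applies to a single test (12/2.5 = 4.8; 28/2.5 = 11.2). In either direction the chance is 24% to 49%. The range rests on assumed common correlations from 0.7 down to 0, on the count of 13, and on reading the printed ≥ as a slip. For that count the figures are upper values.

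Second, the declared and analysed secondaries do not match, and BPI Severity has no named analysis.

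Neither point affects the primary test. This should be corrected before analysis, but it does not undermine the design.

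**What to change.** All changes are to the wording of the analysis plan.

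1. Correct the inequality sign in the decision rule.
2. Make the declared and analysed lists agree, name the instrument for each ANCOVA domain, and add BPI Severity to the repeated-measures analyses.
3. Limit the term statistically significant to the primary and, only if the primary succeeds, to the five declared secondary scores under a prespecified procedure. Holm is one option, with the smallest p value compared with 0.05/5 = 0.01. A fixed sequence starting with BPI is another. The plan ranks only BPI as first, so the order of the rest is for the sponsor to set.
4. Report every other efficacy outcome as an estimate with a 95% confidence interval and a nominal p value labelled exploratory.
5. Leave the safety comparisons unadjusted, so that signals of harm are not hidden.

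The cost is that BDI, AIS, PGI, responder and ANCOVA-domain results can no longer be called significant, and the declared secondaries face a stricter standard. Under Holm the first threshold is lower. Under a fixed sequence each step keeps 0.05, but a failed early step ends later claims.
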